1 STUDY DETAILS

1.1 Study objectives

1.1.1 Primary objective

Primary Objective:	Outcome Measure:
To evaluate the efficacy of anifrolumab plus standard of care (SOC ^a) compared with placebo plus SOC in subjects with active proliferative lupus nephritis (LN) measured by the relative difference in change from baseline to Week 52 in 24-hour urine protein to creatinine ratio (UPCR)	24-hour UPCR

^a Required SOC is described in Section 1.2.1

1.1.2 Secondary objectives

Secondary Objectives:	Outcome Measures:
To evaluate the effect of anifrolumab plus SOC compared with placebo plus SOC ^a on the proportion of subjects achieving Complete Renal Response (CRR) at Week 52	
CRR is defined as meeting all of the following:
 
 • Estimated glomerular filtration rate (eGFR) is 
 – ≥ 60 mL/min/1.73m² or no confirmed decrease of eGFR from baseline of $\geq 20\%$ • 24-hour UPCR ≤ 0.7 mg/mg • No discontinuation of investigational product (IP) or use of restricted medication^b beyond the protocol-allowed threshold before assessment 
eGFR is based on Modification of Diet in Renal Disease (MDRD) formula

^a Required SOC is described in Section 1.2.1

[figure not shown]
[figure not shown]

[figure not shown]

^b Allowed medication are described in Appendix A and Appendix B

1.1.3 Safety objective

Safety Objective:	Outcome Measures:
To characterise the safety and tolerability of anifrolumab	Adverse events (AEs) (including AEs of special interest [AESIs]), vital signs, physical examination, baseline and End of Treatment 12-lead electrocardiograms (ECG), and clinical laboratory tests (haematology, clinical chemistry, urinalysis), Columbia-Suicide Severity Rating Scale (C-SSRS), Personal Health Questionnaire Depression Scale-8 (PHQ-8), extra-renal flares using Systemic Lupus Erythematosus Disease Activity Index 2000 (SLEDAI-2K)-based Flare Assessment Instrument .

1.1.4 Exploratory objectives

Exploratory Objectives:	Outcome Measures:

To evaluate the effect of anifrolumab plus SOC^a compared with placebo plus SOC^a on:
	

CCI [REDACTED]
 
[REDACTED]
 
[REDACTED]
	
[REDACTED]
 
[REDACTED]
 
[REDACTED]
 
[REDACTED]
 
[REDACTED]
 
[REDACTED]
 
[REDACTED]
 
[REDACTED]
 
[REDACTED]
 
[REDACTED]

CCI [REDACTED]
	
[REDACTED]

CCI [REDACTED]
	
[REDACTED]

Proportion of subjects achieving alternative CRR (aCRR) at Week 52 (and Week 104)
 
The difference between the CRR and the aCRR is the addition of a criterion regarding “inactive urine sediment”
	
aCRR is defined as meeting all of the following:
 
 • eGFR is 
 - ≥ 60 mL/min/1.73 m² or no confirmed decrease of eGFR from baseline of $\geq 20\%$ • 24-hour UPCR ≤ 0.7 mg/mg • Inactive urine sediment (defined as < 10 red blood cells [RBC]/hpf) • No discontinuation of IP or use of restricted medication^b beyond the protocol-allowed threshold before assessment 
eGFR is based on MDRD formula

CCI
 	 
 ■  ■  ■  ■  ■  ■ 

Proportion of subjects meeting Graded aCRR at Week 52 (and Week 104)
	
Graded aCRR is defined as meeting both the 24-hour UPCR and eGFR criteria:
 
 • A decrease in 24-hour UPCR: 
 – For subjects with baseline UPCR >3 mg/mg: UPCR ≤1 mg/mg – For subjects with baseline UPCR ≤3 mg/mg: UPCR ≤0.7 mg/mg • eGFR: 
 – ≥60 mL/min/1.73 m² or no confirmed decrease of eGFR from baseline of ≥20% • Inactive urine sediment (defined as <10 RBC/hpf) • No discontinuation of IP or use of restricted medication^b beyond the protocol allowed threshold before assessment

Proportion of subjects able to achieve sustained reduction in oral corticosteroids (OCS) dose at Week 52 or Week 104
	
Sustained reduction of OCS dose:
 
 • Week 52: Prednisone-equivalent dose ≤7.5 mg/day by Week 24 and not exceeding this dose through Week 52 • Week 104: Prednisone-equivalent dose ≤5.0 mg/day by Week 80 and not exceeding this dose through Week 104 
and
 
 • No discontinuation of IP or use of restricted medication^b beyond the protocol-allowed threshold before assessment

Proportion of subjects achieving CRR at Week 52 or Week 104 and achieving sustained reduction of OCS dose	CRR (see definition of CRR above) Sustained reduction of OCS dose (see definition above)

CCI [REDACTED]
	
[REDACTED]

CCI [REDACTED]
	
[REDACTED]

CCI [REDACTED]
	
[REDACTED]

CCI [REDACTED]
	
[REDACTED]

CCI [REDACTED]
	
[REDACTED]

Mean change in scores for overall disease activity from baseline to Week 52 (and to Week 104)
	
SLEDAI-2K

Mean change in score measures of non-renal disease activity from baseline to Week 52 (and to Week 104)
	
Non-renal components of SLEDAI-2K

Mean change in scores for overall disease activity from baseline to Week 52 (and to Week 104)
	
Physician Global Assessment (PGA)

Mean change in the Systemic Lupus International Collaborating Clinics/American College of Rheumatology (SLICC/ACR) Damage Index (SDI) score from baseline to Week 52 (and to Week 104)	SDI
Mean change in scores for patient-reported health status from baseline to Week 52 (and to Week 104)	Patient Global Assessment (PtGA)
To evaluate the immunogenicity of anifrolumab, pharmacokinetics (PK), pharmacodynamics (the PK and immunogenicity results will be reported in the clinical study report)	Anti-drug antibodies (ADA), anifrolumab concentration and PK parameters, 21-gene type I interferon (IFN) gene signature
To evaluate the pharmacokinetics of mycophenolic acid (MPA)	MPA concentration and PK parameters (if applicable)
Mean change in lupus serology from baseline to Week 52 (and to Week 104)	Anti-dsDNA antibodies, C3 and C4 complement levels
CCI	

^a Required SOC is described in Section 1.2.1

^b Allowed medication are described in Appendix A and Appendix B.

^cNote: Spot UPCR will be used instead of 24-hour UPCR for the PRR and CRR classification, when evaluating time to achieve renal response modified to include OCS tapering requirement as well as for the PRR and CRR classification for flare assessment.

1.2 Study design

This is a Phase 2, multi-centre, multinational, randomised, double-blind (prior to the primary analysis), placebo-controlled study to evaluate the efficacy and safety of two IV treatment regimens of anifrolumab versus placebo, while taking protocol-specified SOC treatment with mycophenolate mofetil (MMF) and corticosteroids, in subjects with active biopsy-proven proliferative LN. The study will be performed in adult subjects, 18 to 70 years of age. The study duration is approximately 116 weeks (including screening, treatment and follow-up periods) for those subjects who meet the criteria for the second year extension period and approximately 64 weeks for those subjects who do not meet the criteria for the second year extension period.

[figure not shown]
In this study, approximately 150 subjects will be randomised in a 1:1:1 ratio to receive one of two IV anifrolumab dosing regimens or placebo, which will continue until Week 52, as follows:

- **Basic Regimen:** Anifrolumab 300 mg IV Q4W for 13 doses plus SOC or

- **Intensified Regimen:** Anifrolumab 900 mg IV Q4W for the first 3 doses followed by 300 mg IV Q4W for 10 doses plus SOC or
- **Placebo:** IV Q4W plus SOC

The primary objective will be evaluated at Week 52. After Week 52, eligible subjects will continue with their randomised treatment plus SOC until Week 104. Those subjects not eligible to continue with treatment based on the Week 52 assessments will complete the 8 weeks of additional safety follow-up to complete involvement in the study.

After all randomised subjects have completed the 52-week double-blind period the database will be soft-locked, and the **primary analysis** will be performed, including the assessment of the primary, secondary, exploratory and safety objectives. This analysis will also encompass all available data collected after the 52-week time point. At this stage the Sponsor and Sponsor's delegate who are not directly involved in the management of sites will be unblinded to randomised treatment, but the subjects and investigators will remain blinded (single-blind). The **end of study analysis** will be performed after all subjects have completed the second year extension period, and the database will be locked. One interim analysis may be conducted after approximately 80% of subjects have completed the Week 52 visit or would have completed if they had not discontinued the study. CCI

IP will be administered as an IV infusion via an infusion pump over no less than 60 minutes for the first 3 doses (Visit 1, 2 and 3). Starting with Visit 4, IP can be administered as an IV infusion via an infusion pump over no less than 30 minutes.

Randomisation will be stratified using two factors:

- Results of IFN test at screening using a 4-gene type I IFN test (IFN test-high versus IFN test-low)
- 24-hour UPCR ≤ 3.0 mg/mg versus >3.0 mg/mg (based on 24-hour UPCR performed on a sample obtained within 14 days prior to the expected date of randomisation). Without the results of the second (stratification) sample, subjects cannot be randomised. Turn-around time for results from central laboratory is up to 7 days.

On rare occasion an extension of the 30-day screening window may be allowed if re-collection of the 24-hour UPCR or other required samples is necessary or if the results needed for randomisation are delayed.

Renal biopsy performed within 12 weeks prior to signing the informed consent form (ICF) or during the screening period will be considered as the screening biopsy. Biopsies will be evaluated locally and the local classification will be used to confirm the eligibility criteria.

The biopsy must reveal Class III (\pm class V) or class IV (\pm class V) LN according to the World Health Organisation (WHO) or 2003 International Society of Nephrology/Renal Pathology Society (ISN/RPS) classification. An external renal biopsy adjudication group will adjudicate renal biopsies post-randomisation.

The overall study duration is approximately 116 weeks:

A Screening Period: Up to 30 days

Treatment Period:

The total treatment period is up to 100 weeks (26 doses administered Q4W).

- **52 week double-blind treatment period:** IP will be administered Q4W from Week 0 to Week 48 for a total of 13 doses. The primary endpoint will be evaluated at Week 52.
- **Second year extension period:** At Week 52, eligible subjects will continue treatment with randomised IP (anifrolumab 300 mg or placebo) administration Q4W from Week 52 to Week 100 for a total of 13 doses. The last efficacy assessments will be performed at Week 104.

Follow-up: After the completion of the last IP treatment (Week 48 for subjects who are not participating in the second year extension period and Week 100 for subjects who participate in the second year extension period) subjects will continue in the study for another 12 weeks of safety follow-up after the last administration of IP.

1.2.1 Standard of care immunosuppressive treatment for lupus nephritis

Standard of care treatment for LN will consist of the combination of MMF and corticosteroids. From the day of randomisation onwards until the end of subject's participation in the study including the second year extension period, MMF will be supplied by the Sponsor and Sponsor's delegate to subjects. The target dose of MMF will be 2 gm/day during the first year of the study, where the dose is titrated to the target dose between randomisation and not later than Week 8. It is not mandatory for a subject to receive 2 gm/day of MMF if local treatment standards dictate a lower dose to be given (e.g., for constitutionally small subjects). During the 52-week double-blind treatment period, the minimum dose of MMF is 1.0 gm/day between Week 8 and Week 52. Adjustments of the dose due to suboptimal response, toxicity, or intolerability are allowed if needed. A maximum dose of 3.0 gm/day is allowed up to Week 24 for subjects with suboptimal response between Weeks 8 and 24, which needs to be reduced to ≤ 2.0 gm/day by Week 32. The dose of MMF has to be stable from Week 40 to Week 52.

In the second year, extension period, MMF dose should be ≤ 2.0 gm/day or \leq Week 52 dose, whichever is lower. If MMF dose is > 2.0 gm/day at Week 52, taper to ≤ 2 gm/day will be required by Week 60. Failure to do so will lead to withdrawal from IP. A decrease in MMF dose is allowed at the investigator's discretion between Week 52 to Week 92. The dose of MMF must be stable from Week 92 to Week 104.

Subjects may enter the study taking daily OCS at a maximum dose of 0.5 mg/kg/day of prednisone-equivalent not to exceed 40 mg/day. In addition, subjects will receive IV (or oral,

if applicable) methylprednisolone pulse 500 mg on the day of randomisation, prior to receiving the IP, unless they have received a methylprednisolone pulse of ≥ 500 mg within 10 days prior to randomisation. Subjects may receive one additional (optional) dose of IV (or oral, if applicable) methylprednisolone pulse (≤ 500 mg) for renal or extra-renal disease activity after the Week 0 (Day 1) visit up to and including the Week 8 visit. Methylprednisolone pulse can be administered on two consecutive days but the cumulative dose must not exceed 500 mg.

Details on other medications permitted during the study are given in [Appendix A](#) to [Appendix C](#).

1.2.2 Oral corticosteroid burst and taper

From randomisation to Week 40, subjects may receive 1 burst of OCS for increased extra renal SLE disease activity or for non-SLE activity. Subjects who receive more than 1 burst during this time may continue in the study but will be considered non-responders (based on the conditions in [Appendix B](#)) for subsequent responder analyses (such as CRR), regardless of whether the burst was administered for increased SLE or non-SLE activity. No increase in OCS is allowed from Week 40 until Week 52 assessment. One burst and taper is allowed between Week 52 and Week 92. Further details are given in [Appendix B](#).

1.2.3 Protocol-specified oral corticosteroid tapering for the double-blind treatment period

OCS tapering is required during the study with the goal of tapering OCS to prednisone-equivalent of ≤ 10 mg/day by Week 12 and prednisone-equivalent of ≤ 7.5 mg/day by Week 24. If subjects experience an increase in SLE disease activity upon tapering of OCS their dose may be returned to a dose less than or equal to the dose prior to the taper. The return to the pre-taper dose will not be considered an OCS “burst and taper” (see Section [1.2.2](#)).

Subjects who are unable to taper OCS to ≤ 15 mg/day at Week 12 or < 15 mg/day at Week 24 will be discontinued from IP treatment. However, subjects who exceed the maximum daily OCS dose at the Week 12 or Week 24 visits may continue to receive IP if the current dose is part of a protocol allowed temporary OCS dose (e.g., burst and taper) increase. Subjects who cannot be returned to their pre-increase dose within 14 days from the start of burst will have their investigational product discontinued at the next visit.

The subjects discontinued from IP treatment before Week 48 will be followed until Week 52 (or for a minimum of 12 weeks after last dose of investigational product for subjects for whom IP was discontinued within 12 weeks prior to Week 52).

Investigators will not be required, but may continue, to taper OCS dose beyond the target of 7.5 mg/day up to Week 40. Steroid tapering will not be permitted between Week 40 and Week 52. After the Week 52 primary endpoint assessments are completed additional OCS tapering can be done.

1.2.4 Management of oral corticosteroids during the second year extension period

The following rules apply to OCS during the second year extension period. Further details are provided in [Appendix B](#).

- If OCS >7.5mg/day at Week 52, tapering to ≤7.5mg/day is required by Week 60. Failure to achieve ≤7.5 mg/day by Week 60 will lead to discontinuation from IP.
- OCS tapering goal ≤5 mg/day at Week 80. Tapering below 5 mg/day is allowed any time until Week 92.
- No change in OCS dose will be allowed from Week 92 to Week 104.
- One burst and taper is allowed between Week 52 and Week 92.

1.2.5 Discontinuation of IP

Criteria for discontinuing IP for worsening of LN or SLE (at any time):

Blinded IP will be discontinued in subjects who meet pre-defined criteria for worsening LN or SLE. Subjects may receive rescue treatment as clinically indicated. Subjects who had their IP discontinued will be followed according to the study schedule and should have a 24-hour UPCR measurement within 4 weeks of the decision to discontinue IP and before the start of a new treatment for LN. These subjects will be followed until Week 52 (or for a minimum of 12 weeks after last dose of IP for subjects for whom IP was discontinued within 12 weeks prior to Week 52). If discontinuation occurs during the second year extension period, subjects will be followed until Week 104 (or for a minimum of 12 weeks after last dose of IP for subjects for whom IP was discontinued within 12 weeks prior to Week 104).

- >30% decrease in eGFR compared to baseline due to LN **and** eGFR <60 mL/min/1.73 m² (on two independent samples) **or**
- Increase in renal or extra renal lupus activity requiring prohibited systemic immunosuppressive treatment (e.g. cyclophosphamide, rituximab, belimumab)
- Receipt of >1 methylprednisolone pulse after the day of randomisation
- Receipt of any methylprednisolone pulse after Week 8
- The IP will be discontinued if MMF is discontinued and another immunosuppressant is initiated

Criteria for discontinuation of IP for worsening of LN or SLE at Week 12 and Week 24:

- eGFR <75% of baseline and <60 mL/min/1.73 m² (on two independent samples) **or**
- Nephrotic range UPCR (confirmed by a second measurement at least two weeks after the first measurement):

- Subjects with 24-hour UPCR ≤ 3 mg/mg at baseline will be withdrawn if 24-hour UPCR increases by $>50\%$ from baseline to >3.5 mg/mg
- Subjects with 24-hour UPCR >3 mg/mg at baseline will be withdrawn if 24-hour UPCR at Week 24 >3.5 mg/mg and there is $<60\%$ improvement from baseline **or**
- Inability to adhere to corticosteroids requirements:
 - Inability to reduce OCS to ≤ 15 mg/day prednisone-equivalent at Week 12
 - Inability to reduce OCS to <15 mg/day by Week 24

Subjects who exceed the maximum daily OCS dose at the Week 12 or Week 24 visits may continue to receive IP if the current dose is part of a temporary increase in OCS dose (e.g., protocol-allowed burst and taper). Subjects who cannot be returned to their pre-increase dose within 14 days from the start of increase will have their IP discontinued at the next visit.

Criteria for discontinuing IP at Week 52:

Subjects not meeting the criteria to continue for the second year extension period will not receive any IP at Week 52 and will complete the study after completing the required follow-up visits.

Subjects meeting the following criteria may continue to receive blinded IP between Weeks 52 and 100.

- (i) Meeting all of the following criteria based on the renal portion of the PRR definition:
 - eGFR is:
 - ≥ 60 mL/min/1.73 m² or no confirmed decrease of eGFR from baseline of $\geq 20\%$
 - Improvement in 24-hour UPCR:
 - For subjects with a baseline UPCR ≤ 3 mg/mg: <1.0 mg/mg
 - For subjects with a baseline UPCR >3 mg/mg: $>50\%$ improvement from baseline and ≤ 3.0 mg/mg

Renal discontinuation criteria must be confirmed in two separate samples. The second measurement should be at least 1 week after the first measurement.

- (ii) No discontinuation of IP.
- (iii) Negative HIV test after signed the Main ICF

Criteria for discontinuing IP at Week 52, Week 56 or Week 60:

- Failure to obtain Pap smear after Week 48 with result available at Week 60 at latest

- Pap smear result not meeting the eligibility criteria (see Appendix K of the Protocol) at Week 52, 56, or 60 of a Pap smear obtained after Week 48
- Failure to obtain Week 52 QuantiFERON test result by Week 56

Criteria for discontinuing IP at Week 60 and later:

- OCS >7.5 mg/day (except one OCS burst and taper)
- MMF >2 gm/day or >Week 52 dose, if Week 52 dose <2 gm/day

Subjects who discontinue the IP during the second year extension period will be followed until Week 104 (or for a minimum of 12 weeks after last dose of IP for subjects for whom IP was discontinued within 12 weeks of Week 104).

Criteria for discontinuation of IP for reasons other than lack of efficacy at any time during the study:

1. Subject decision: The subject is at any time free to discontinue treatment, without prejudice to further treatment. The primary reason should be documented as one of the following:
 - (a) Subject is unable to comply with protocol-specified visits and/or procedures due to conflicts not related to clinical study
 - (b) An AE or laboratory abnormality is of concern to the subject, but not clinically significant to physician
 - (c) The subject is concerned about possibility of receiving placebo or ineffective treatment
 - (d) Subject wishes to participate in another clinical study
 - (e) Subject is interested in taking a treatment that is not allowed in this study
 - (f) Subject perceives logistics at the clinical site to be unacceptable
 - (g) Other reason
2. Lost to follow-up
3. Adverse event that, in the opinion of the Investigator of the Sponsor and Sponsor's delegate/Designee Medical Monitor, contraindicates further dosing with IP
4. Severe non-compliance with the study protocol
5. The Investigator or Sponsor and Sponsor's delegate/Designee Medical Monitor deems withdrawal as being in the subject's best interest

6. Pregnancy, positive pregnancy test, or subject expresses an interest in becoming pregnant
7. Isolated HBcAb positivity with HBV DNA above the LLOQ confirmed by the central laboratory
8. Positive HIV test
9. Receipt of any excluded medications
10. The use of restricted medications if the Sponsor and Sponsor's delegate/Designee Medical Monitor, in consultation with the Sponsor and Sponsor's delegate, determines the subject must be discontinued
11. A diagnosis of active TB, premature discontinuation of treatment for latent TB, or noncompliance with latent TB therapy. Note: Duration of treatment for latent TB should follow the local practice. If local practice is not defined, then Centers for Disease Control and Prevention (CDC) guidance for immunocompromised patients should be used.
12. Subject is unblinded by the Investigator

Additional restrictions related to concomitant medications are discussed in [Appendix A](#) and [Appendix B](#).

Further details can be found in Section 3.9.4 of the clinical study protocol.

1.3 Number of subjects

A total of approximately 150 subjects will be randomised 1:1:1 to receive one of the two IV anifrolumab dosing regimens (Basic Regimen or Intensified Regimen) or placebo.

The sample size is based on the following assumptions:

- Reductions from baseline to Week 52 in 24-hour UPCR of 65% and 46% for the anifrolumab and placebo arms, respectively (i.e., ratios of 24-hours UPCR from Week 52 to baseline of 0.35 and 0.54, respectively), based on data presented in (Furie R, 2014).
- The change from baseline in the log-transformed 24-hour UPCR values follow a normal distribution with a standard deviation (SD) of 0.8, based on data from the anifrolumab Phase 2b study (CD1013)

Based on these assumptions, a sample size of 50 subjects per arm would result in an observed relative difference in the change from baseline to Week 52 in 24-hour UPCR of 0.65 (here expressed as the ratio, comparing anifrolumab to placebo), and a corresponding 95% confidence interval (CI) of (0.50, 0.85) comparing the pooled anifrolumab group (Basic and Intensified) with placebo group. Under the assumption that the interim analysis is performed

with 120 subjects, a 0.001 2-sided alpha will be spent, and the final analysis will be based on a 2-sided alpha of 0.0499 (East Version 6.4). If the study is not stopped for futility, this sample size provides approximately 87% power for the primary analysis with a 2-sided alpha of 0.0499 to reject the hypothesis of no effect (relative difference =1) for comparing the pooled anifrolumab treatment group with placebo. The minimal detectable relative difference in the change from baseline to Week 52 in 24-hour UPCR between the pooled anifrolumab treatment group versus placebo is approximately 0.76, corresponding to a reduction from baseline to Week 52 in 24-hour UPCR of 59% in the pooled anifrolumab group (ratio of 24-hour UPCR from Week 52 to baseline of 0.41).

Based on the above assumptions, if a futility analysis is performed with a boundary for the predictive power of 20% and supposing that 120 subjects will be included in the interim analysis and 150 subjects at the final analysis, the corresponding treatment effect boundary for relative difference in the change from baseline to Week 52 in 24-hour UPCR between the pooled anifrolumab treatment group versus placebo will be 0.81. This would result in an overall power of 86% (to continue the study after the futility analysis and reject the hypothesis of no effect with a 2-sided alpha of 0.0499).

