3.9 Discontinuation of investigational product

3.9.1 Criteria for discontinuation of investigational product due to worsening LN or SLE (at any time)

Blinded IP will be discontinued in subjects who meet pre-defined criteria for worsening LN or SLE. Subjects may receive rescue treatment as clinically indicated. Subjects who had their IP discontinued will be followed according to the study schedule. These subjects will be followed until Week 52 (or for a minimum of 12 weeks after last dose of IP for subjects for whom IP was discontinued within 12 weeks prior to Week 52). If discontinuation occurs during the second year extension period, subjects will be followed until Week 104 (or for a minimum of 12 weeks after last dose of IP for subjects for whom IP was discontinued within 12 weeks prior to Week 104).

- >30% decrease in eGFR compared to baseline due to LN and eGFR <60 mL/min/1.73 m² (on two independent samples) or
- Increase in renal or extra-renal lupus activity requiring prohibited systemic immunosuppressive treatment (eg, cyclophosphamide, rituximab, belimumab)
- Receipt of >1 methylprednisolone pulse after the day of randomisation
- Receipt of any methylprednisolone pulse after Week 8
- The IP will be discontinued if MMF is discontinued and another immunosuppressant is initiated

3.9.2 Criteria for discontinuation of investigational product for worsening of LN or SLE at Week 12 and Week 24

- eGFR <75% of baseline and <60 mL/min/1.73 m² (on two independent samples) or
- Nephrotic range UPCR (confirmed by a second measurement at least two weeks after the first measurement):
 - Subjects with 24-hour UPCR ≤3 mg/mg at baseline will be withdrawn if 24-hour UPCR increases by >50% from baseline to >3.5 mg/mg

- Subjects with 24-hour UPCR >3 mg/mg at baseline will be withdrawn if 24-hour UPCR at Week 24 >3.5 mg/mg and there is $<60\%$ improvement from baseline or
- Inability to adhere to corticosteroids requirements:
 - Inability to reduce OCS to ≤ 15 mg/day prednisone-equivalent at Week 12
 - Inability to reduce OCS to <15 mg/day by Week 24

Subjects who exceed the maximum daily OCS dose at the Week 12 or Week 24 visits may continue to receive IP if the current dose is part of a temporary increase in OCS dose (eg, protocol-allowed burst and taper). Subjects who cannot be returned to their pre-increase dose within 14 days from the start of the increase will have their IP discontinued at the next visit.

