4.2 Analysis methods

4.2.1 Analysis of the primary variable

The primary estimand is evaluating the efficacy on disease activity of the pooled anifrolumab groups relative to placebo in subjects with active proliferative LN. This is measured by the

relative difference in change from baseline to Week 52 in the 24-hour UPCR. The full analysis set (as defined in Section 2.1.2) will be used, and any data collected after IP discontinuation will be excluded from the analysis, in order to reflect the effect of the initially assigned and dosed IP (anifrolumab or placebo), prior to the occurrence of the intercurrent event of IP discontinuation, applying a “while on treatment” estimand strategy. The individual anifrolumab regimens will also be assessed but not as part of the primary analysis.

The estimand for all continuous endpoints (including the primary endpoint) follows the “while on treatment” strategy, which includes data only up to IP discontinuation. If IP has not been reported as prematurely discontinued, available data up to and including Week 104 will be used for continuous endpoints analyses. Otherwise, the date of IP discontinuation will be determined as the date of last IP administration. However, all subjects who have an infusion of IP within the Week 48 analysis visit window will be determined to have completed treatment in the double-blind treatment period, and their Week 52 data will be included in the analyses.

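### The SAP's 87% power, 86% overall power and 0.76 minimal detectable ratio count all 150 subjects at Week 52, with no allowance for values the primary analysis excludes after IP discontinuation

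*SAP*

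**What the plan says.** SAP Section 1.3 sets the size: "A total of approximately 150 subjects will be randomised 1:1:1". Pooling the two regimens gives 100 against 50. The inputs are "ratios of 24-hours UPCR from Week 52 to baseline of 0.35 and 0.54, respectively", which the section rounds to a relative difference of 0.65, and changes in log UPCR that "follow a normal distribution with a standard deviation (SD) of 0.8". With a two-sided alpha of 0.0499, "this sample size provides approximately 87% power for the primary analysis". The minimal detectable ratio is given as about 0.76.

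The futility paragraph works from "supposing that 120 subjects will be included in the interim analysis and 150 subjects at the final analysis", gives a treatment-effect boundary of 0.81, and concludes: "This would result in an overall power of 86" (per cent). Neither SAP Section 1.3 nor Protocol Section 8.2 makes an allowance for discontinuation.

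For the primary analysis, SAP Section 4.2.1 states that "any data collected after IP discontinuation will be excluded from the analysis". Discontinuation is dated to the last infusion. Subjects infused in the Week 48 window count as having completed treatment and keep their Week 52 value. The analysis of all collected data is a sensitivity analysis only.

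Protocol Section 3.9.1 states: "Blinded IP will be discontinued in subjects who meet pre-defined criteria for worsening LN or SLE". Sections 3.9.1 and 3.9.2 list the renal, immunosuppressant and corticosteroid criteria, and Section 3.9.4 adds other reasons.

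**The concern.** The number of subjects behind the power statement and the number the primary analysis can use at Week 52 come from different rules. If all data counted, subjects who stop IP and are followed to Week 52 could still supply the endpoint, and 150 would be a reasonable count apart from withdrawals. With off-IP data excluded, anyone whose last infusion falls before the Week 48 window has no Week 52 value in the primary analysis, even if the sample was taken.

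Section 1.3 uses the later interim size (120 subjects) and the matching alpha (0.0499, against 0.049 in Protocol Section 8.2), but it does not reflect this exclusion. At stake is how a non-significant primary result is read: it would be set against a power figure that takes no account of the excluded values. The minimal detectable ratio and the overall power with futility share the problem.

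**Working it through.** **Inputs.** From SAP Section 1.3: 100 against 50 subjects, SD 0.8 on the log scale, ratio 0.65 (ln 0.65 = -0.431), two-sided alpha 0.0499. Assumed here, because the documents give no rate: a fraction of 10, 20 or 30% without an on-IP Week 52 value, equal across arms. Write f for the fraction retained.

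**Reproducing the plan's figures (f = 1).**
- SE = 0.8 × √(1/100 + 1/50) = 0.1386.
- Power: noncentrality 0.431/0.1386 = 3.11. The noncentral t with 148 df gives 87.0%. (The unrounded ratio 0.35/0.54 = 0.648 gives 87.5%.)
- 95% CI: exp(-0.431 ± 1.96 × 0.1386) = 0.50 to 0.85, as stated.
- Minimal detectable ratio: exp(-1.96 × 0.1386) = 0.76, as stated.
- Futility boundary, with 80 against 40 at the interim (SE 0.1549) and information fraction 0.8: exp{(-1.961 + 0.842 × √(1/0.8 - 1)) × √0.8 × 0.1549} = exp(-0.213) = 0.81, as stated.
- Overall power: the probability of passing that boundary and then rejecting, from the bivariate normal with correlation √0.8, is 86%, as stated.

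Every figure therefore rests on the full 150.

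**With values lost.** SE = 0.8 × √(1/(100f) + 1/(50f)). The futility column applies the same loss at both looks, so the information fraction stays at 0.8.

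| Loss | n analysed | SE | Power | Minimal detectable ratio | Overall power with futility |
|---|---|---|---|---|---|
| 0% | 100 / 50 | 0.139 | 87.0% | 0.76 | about 86% |
| 10% | 90 / 45 | 0.146 | 83.3% | 0.75 | about 82% |
| 20% | 80 / 40 | 0.155 | 78.7% | 0.74 | about 78% |
| 30% | 70 / 35 | 0.166 | 73.1% | 0.72 | about 72% |

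Unequal loss shifts the result. At ratio 0.648, equal 20% loss gives 79.3%; 30% on placebo with 15% on anifrolumab gives 76.3%; 15% with 22.5% gives 80.4%.

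**Residual SD that would hold 87%.** 0.8 × √f = 0.76, 0.72 and 0.67 at 10, 20 and 30% loss.

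**Recovery through the MMRM.** Assume stopping spread evenly after Weeks 12, 24 and 36, and equal correlation between visits of 0.3 to 0.8. At 20% loss the effective fraction of Week 52 information is 0.82 to 0.93, and power about 80 to 85%. At 10% it is about 84 to 86%, and at 30% about 75 to 83%.

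**Recovery through baseline adjustment.** Take 0.8 as the SD of change, as the SAP does. If baseline and Week 52 log values have equal variance and correlation ρ, the residual variance after adjustment is 0.32 × (1 + ρ). For ρ = 0.3, 0.5 and 0.7 the residual SD is 0.645, 0.693 and 0.738, and power at 20% loss is 92.8, 88.9 and 84.9%. If the Week 52 SD is 1.5 to 2 times the baseline SD, power over the same correlations is about 79 to 84%. With a factor of 2 and ρ = 0.5 the residual SD is 0.80, so there is no gain.

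**The case against.** The strongest reply is that Section 1.3 is correct on its own terms. It is conditional on listed assumptions, says approximately, and its arithmetic reproduces. A reader might infer a calculation error; there is none. What is missing is an allowance.

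A reader might also infer that the trial's real power is about 79%. The documents do not support that. No document states a 20% stopping rate, and the stopping rules do not show how often they will apply. The 79% also comes from an unadjusted two-sample comparison in which subjects who stop contribute nothing. The specified model is an MMRM that keeps on-IP values from Weeks 12, 24 and 36 and adjusts for log baseline UPCR and the stratification factors. For a given equal loss, the table is therefore close to a floor, and baseline adjustment alone could take power above 87%.

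Other text limits the loss. The Week 48 rule protects late stoppers. Some subjects who use restricted medication or cannot tolerate MMF may stay on IP (Protocol Sections 7.7.2.2 and 7.7.3.1). The futility calculation in SAP Section 5.1 can use the MMRM standard error, so the interim decision does not depend only on the planned 0.81.

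These points stand, and they rule out a single corrected figure. They do not support leaving 87% unqualified. The SAP states an SD of 0.8, gives no adjusted residual SD, and claims no gain from adjustment. MMRM recovery alone stays below 87% in every case above. It is limited further because discontinuation is dated to the last infusion, so a UPCR taken after that dose is dropped, including the sample Protocol Section 4.2.2 requests within 4 weeks of the decision to stop.

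**Conclusion.** The point holds as a gap in the stated basis for power. The 87%, the 86% and the 0.76 each require a Week 52 value from every one of 150 subjects, while the primary analysis excludes such values for anyone who stops IP before the Week 48 window. At assumed equal losses of 10, 20 and 30%, with SD 0.8 and ratio 0.65, power is about 83, 79 and 73% before recovery. The minimal detectable ratio moves less, to 0.75, 0.74 and 0.72.

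Whether the primary analysis falls short of 87% cannot be settled from the documents. That depends on the discontinuation rate, its balance between arms, the correlations between visits and the baseline-adjusted residual SD, none of which is given. The figures also hold the effect and SD fixed. Selective stopping, or leaving out values taken after rescue treatment, could move either in an unknown direction.

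**What to change.** Restate SAP Section 1.3 as a short table. For 0, 10, 20 and 30% of subjects without an on-IP Week 52 value, give power, the minimal detectable ratio and the overall power with futility. Do this at SD 0.8 and again at a stated baseline-adjusted residual SD, with its source. If credit is taken for earlier visits in the MMRM, state the assumed correlations and timing of stopping.

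The cost is SAP wording and a few calculations. Enrolment, the test and the alpha do not change. The downside is that the stated power may become less favourable; if the sourced residual SD is low enough, it may not.
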